[name] at the University of California San Francisco has reported on his initial 50 patients treated with the Zenith t-Branch device. All patients were considered to be at elevated risk for open repair. His group recently published a subsequent report of 81 patients, some of whom were included in the initial reports. In these reports, he has demonstrated excellent effectiveness and safety, with 100% implant success, 4% peri-operative mortality, and 6% overall aneurysm related mortality. Among the first 22 patients, there was a 41% incidence of major morbidity. All patients suffered from “some combination of fever, leukocytosis, anorexia, malaise, thrombocytopenia and coagulopathy.” The most recent series reports a 3.7% incidence of permanent paralysis and a 20% incidence of temporary spinal cord injury, all of which occurred in the peri-operative period. These data demonstrate that the operation can be done safely in very sick patients, but that medical complications are common and are to be expected. In this report, there was a high incidence of re-intervention at 40%. Most of these reinterventions were performed endovascularly or were minor surgical procedures at access site and were well tolerated by the patients. Overall, 90% of the patients were “treated without procedure-related death, dialysis, paralysis, aneurysm rupture, or conversion to open repair.”

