### 8.9 Adverse Events

An adverse event is any new, undesirable medical occurrence or change (worsening) of a pre-existing condition that occurs in a patient, whether or not considered to be associated with the

product. Elective hospitalizations for pre-existing conditions are not adverse events. Requirements for reporting AEs are dependent upon the reviewing IRB policy. Adverse events will be reviewed by a Clinical Events Committee (CEC). The CEC will meet periodically, a minimum of annually. Adverse Event information is recorded in the **Adverse Event CRF**.

For purposes of this study, the following events are not considered adverse events, because they are expected to occur in conjunction with the index procedure or are associated with customary, standard care of patients undergoing endovascular TAAA repair procedures:

- Early post-operative pain (within 72 hours of index procedure) at the access site and/or related to position on procedure table (i.e. low back pain, abdominal pain, groin pain)
- Post-anesthesia/conscious sedation emesis, nausea, or headache (within 72 hours of index procedure)
- Electrolyte imbalance without clinical sequelae following index procedure, even if requiring correction
- Low grade temperature increase (< 100.5 °F)
- Blood loss not requiring transfusion
- Minor, localized tenderness, swelling, induration, bruising, erythema, hematoma etc. at vascular access site that does not require surgical intervention, evacuation, transfusion, or antibiotics
- Non-sustained arrhythmia not requiring treatment or intervention
- Prophylactic administration of atropine
- Prophylactic pacing
- Isolated, non-sustained PVCs/PACs
- Asymptomatic hypotension or hypertension
- Use of vaso-active medications for asymptomatic hypotension in the setting of routine spinal cord protection
- Atelectasis not requiring treatment
- Pleural effusion(s) not requiring treatment
- Urinary retention or hematuria not requiring intervention other than urinary drainage
- Thrombocytopenia not requiring transfusion
- Leukocytosis not requiring treatment
- Delirium, confusion or agitation within the first 72 hours postoperative unless such is found to be attributable to a TIA or Stroke or other new medical condition
- Constipation
- Chest pain that is determined to be non-cardiac in origin
- Peripheral edema not requiring treatment other than diuresis
- Shortness of breath not requiring treatment other than diuresis
- Bruising

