- Loss of appetite/anorexia requiring medical treatment
- Weakness not due to spinal cord injury (i.e. fatigue and deconditioning)

The Investigator and/or IRB may require that these events are reported as adverse events. In this case, the Investigator will report these observations based on his medical judgment and requirements of the IRB.

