**1.2 Adverse Event and Serious Adverse Event Collection and Reporting**

An adverse event (AE) is any new, undesirable medical occurrence or change (worsening) of a pre-existing condition that occurs in a patient, whether or not considered to be associated with the product. Elective hospitalizations for pre-existing conditions (e.g., elective cosmetic procedures) are not adverse events. Requirements for reporting AEs are dependent upon the reviewing IRB policy. Adverse events will be reviewed by a Clinical Events Committee (CEC). The CEC will meet periodically, a minimum of annually. Adverse Event information is recorded in the **Adverse Event Case Report Form (CRF)**.

For purposes of this study, the following events are not considered adverse events, because they are expected to occur in conjunction with the index procedure or are associated with customary, standard care of patients undergoing endovascular AAA repair procedures:

- Early post-operative pain (within 72 hours of index procedure) at the access site and/or related to position on procedure table (i.e. low back pain)
- Post-anesthesia/conscious sedation emesis, nausea, or headache (within -72 hours of index procedure)
- Electrolyte imbalance without clinical sequelae following index procedure, even if requiring correction
- Low grade temperature increase (< 100.5 °F)
- Blood loss not requiring transfusion and not resulting in decreased hematocrit.

- Minor, localized tenderness, swelling, induration, bruising, erythema, hematoma etc. at vascular access site that does not require surgical intervention, evacuation, transfusion, or antibiotics
- Non-sustained arrhythmia not requiring treatment or intervention
- Prophylactic administration of atropine
- Prophylactic pacing
- Isolated, non-sustained PVCs/PACs
- Asymptomatic hypotension or hypertension
- Use of pressor medications for asymptomatic hypotension in the setting of routine spinal cord protection
- Atelectasis not requiring treatment
- Urinary retention or hematuria not requiring intervention other than urinary drainage
- Thrombocytopenia not requiring transfusion
- Mild leukocytosis not requiring treatment

The Investigator and/or IRB may require that these events are reported as adverse events. In this case, the Investigator will report these observations based on his medical judgment and requirements of the IRB.

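### Protocol section 8.9 and Appendix IX section 1.2 give conflicting lists of events not counted as adverse events, and the anorexia and blood-loss items in 8.9 need reconciling

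*Protocol*

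**What the plan says.** Section 8.9 defines an adverse event broadly and then carves out a list with the words "the following events are not considered adverse events, because they are expected to occur in conjunction with the index procedure". Appendix IX, section 1.2, repeats the definition and that lead-in, except that it ends by referring to AAA rather than TAAA repair. Both sections send adverse events to the same Adverse Event CRF and to the same CEC.

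The lists then part. Section 8.9 includes, for example, "Pleural effusion(s) not requiring treatment", "Delirium, confusion or agitation within the first 72 hours postoperative" (unless traced to a TIA, stroke or other new condition), "Shortness of breath not requiring treatment other than diuresis" and "Chest pain that is determined to be non-cardiac in origin". Appendix IX has none of these. Appendix IX exempts "Mild leukocytosis not requiring treatment", while 8.9 exempts untreated leukocytosis of any severity. Section 8.9 also exempts "Loss of appetite/anorexia requiring medical treatment"; Appendix IX has no anorexia item.

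Both sections allow the investigator or the IRB to require that listed events be reported after all. Neither says which list prevails.

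Sections 8.11 and 9.1.1 list nine MAEs for the primary safety endpoint, one of which is procedural blood loss of at least 1,000 cc. Sections 8.11 and 12.2 let the CEC decide which further adverse events count as MAEs.

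**The concern.** The two sections set different rules for one data field. Staff who follow 8.9 would leave an untreated pleural effusion off the Adverse Event CRF; staff who follow the monitoring plan would record it. In an open, single-arm, single-institution study there is no control group with the same recording rule against which an inconsistency would cancel, so adverse event rates mean something only if the rule is fixed.

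Two items in 8.9 are a problem even without the second list. As written, the anorexia item exempts the case that needs treatment and leaves the case that does not need it unexempted. The blood-loss item turns on transfusion alone, so it overlaps with an event that the protocol names as major.

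At stake are the count of non-serious adverse events and the pool of events from which the CEC may add MAEs.

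**Working it through.** The protocol states no item count, so there is no figure of its own to reproduce. The check is a count and a side-by-side reading.

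**Step 1: count.** Section 8.9 has 25 items and Appendix IX 1.2 has 16. Each of the 16 has a counterpart in 8.9, so 25 − 16 = 9 items stand only in 8.9.

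**Step 2: the nine items, with the limits 8.9 puts on them.**

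| Exempt only in 8.9 | Limit stated in 8.9 |
|---|---|
| Pleural effusion | No treatment needed |
| Delirium, confusion, agitation | First 72 hours; not due to TIA, stroke or another new condition |
| Constipation | None |
| Chest pain | Judged non-cardiac |
| Peripheral edema | No treatment beyond diuresis |
| Shortness of breath | No treatment beyond diuresis |
| Bruising | None (Appendix IX exempts only minor bruising at the access site) |
| Loss of appetite, anorexia | Treatment **is** needed |
| Weakness | Not due to spinal cord injury |

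**Step 3: shared items that differ in scope.**

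| Item | 8.9 | Appendix IX 1.2 |
|---|---|---|
| Leukocytosis | Untreated, any severity | Untreated and mild |
| Blood loss | No transfusion | No transfusion and no fall in hematocrit |
| Early pain, examples | Low back, abdominal, groin | Low back |

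**Step 4: follow one event through both rules.** Take blood loss that is not transfused but lowers the hematocrit. Section 8.9 exempts it. It fails the second condition in Appendix IX, so there the general definition applies and it is an adverse event. The same happens with an untreated effusion, non-cardiac chest pain, or marked but untreated leukocytosis.

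**Step 5: the anorexia item against the rest of 8.9.** Twelve items state a condition about treatment or intervention.
- Ten exempt the event only if treatment is absent or limited: blood loss, access-site findings, arrhythmia, atelectasis, pleural effusion, urinary retention or hematuria, thrombocytopenia, leukocytosis, edema and shortness of breath.
- One, electrolyte imbalance, exempts the event even when corrected, but only if there are no clinical sequelae.
- One, anorexia, exempts the event when treatment is needed, with no further limit.

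10 + 1 + 1 = 12. The anorexia item is alone in making treatment the condition for exemption. Read literally, non-serious treated anorexia need not be recorded and untreated anorexia must be.

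**Step 6: blood loss against the MAE list.** The 8.9 exemption has no volume limit. A procedural loss of at least 1,000 cc without transfusion is therefore not an adverse event under 8.9 and is an MAE under 8.11 and 9.1.1.

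**Step 7: what depends on the list.** The nine named MAEs do not refer to it. The effectiveness composite and the secondary endpoints do not use overall adverse event counts. What does depend on it is the record of non-serious adverse events and, through 8.11 and 12.2, the set of adverse events the CEC can consider for MAE status.

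**The case against.** The strongest reply is that this is housekeeping. The nine named MAEs count on their own terms. Estimated blood loss is captured on the procedure form under section 6.3, so a loss of at least 1,000 cc can be found whatever the adverse event list says. Anything serious is recorded on the Adverse Event CRF under 8.10, and the investigator or IRB may require listed events to be reported. Section 12.2 describes CEC adjudication as covering device-related and serious events, and constipation or bruising would rarely be either. Section 8.9 also exempts some treated events elsewhere, such as corrected electrolytes and edema managed by diuresis.

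Most of this stands, and it limits the point. It does not remove it: the clause on the investigator and IRB makes recording discretionary and does not choose a list, and two incompatible rules still apply to one form.

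Several stronger readings are tempting, and the document does not support them:
- **A large share of the 60 subjects is affected.** A reader might infer this from section 2.1.4, where a cited series reports that all patients had "some combination of fever, leukocytosis, anorexia, malaise, thrombocytopenia and coagulopathy". The series gives no rate for any single finding, and the sentence follows one about the first 22 patients, so its denominator is unclear. Of the six findings, thrombocytopenia is worded alike in both lists and low-grade temperature has the same limit in both. Malaise and coagulopathy are named in neither. Only leukocytosis and anorexia differ.
- **Treated anorexia disappears from the safety data.** The serious-event route and the reporting clause prevent that conclusion. At most, non-serious treated anorexia may go unrecorded.
- **The two lists contradict each other on anorexia in opposite directions.** Appendix IX has no anorexia item, so the oddity is internal to 8.9.
- **The monitor and the study file hold different datasets.** Both sections point to one CRF, and no separate dataset is described.

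**Conclusion.** The point holds as a minor but real contradiction. Nine of the 25 items in 8.9 have no equivalent exemption in Appendix IX, and three shared items differ in scope. The anorexia item runs against the pattern of its own list, and the blood-loss item in 8.9 overlaps with a named MAE.

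The consequence is confined to counts of non-serious adverse events and, indirectly, to what may reach the CEC for possible MAE classification. A reader might infer that the primary 30-day safety endpoint changes with the list. It does not do so directly, because its nine components are named separately. The number of subjects affected cannot be derived from the document.

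The conclusion rests on reading both lists literally and on neither section taking precedence, since none is stated. That a word was dropped from the anorexia item is likely but not confirmed.

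**What to change.** - Use one reconciled list in section 8.9 and Appendix IX 1.2, or keep it in one place and refer to it from the other. Settle the nine items found only in 8.9 and the wording of leukocytosis, blood loss and early pain.
- Check the anorexia item against its intended meaning. If a negative was dropped, restore it; if treated anorexia was meant to be exempt, say so and give the reason.
- Add one sentence that no event meeting the SAE or MAE definition is excluded by the list. This also resolves the overlap with blood loss of at least 1,000 cc.

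The cost is wording in two places and possibly a few more minor adverse events recorded. If subjects are already enrolled, note which list has been applied to the data so far.

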### **8.10 Serious Adverse Events (SAE)**

A serious adverse event (SAE) is defined as one that suggests a significant hazard or side effect, regardless of the investigator's opinion on the relationship to the investigation. This includes, but may not be limited to, any event that:

- Is fatal
- Is life-threatening
- Requires or prolongs (>24 hours) inpatient hospitalization
- Is a persistent or significant disability or incapacity
- Is considered an important medical event

Important medical events may be considered serious by the investigator although they may not be immediately life threatening or result in death or prolong hospitalization. Such important medical events are those that may jeopardize the patient, require intervention to prevent one of the outcomes listed above, or result in urgent investigation. Examples include, but are not limited to, allergic bronchospasm, convulsions, and blood dyscrasias.

Serious Adverse Events will be recorded in the **Adverse Event CRF**. The investigator is also required to adhere to the reviewing IRB requirements for reporting of SAEs.

### **8.11 Major Adverse Events (MAE)**

The following specific events will be considered major adverse events (MAE) for the purpose of evaluating the primary (30 day) and secondary (1 year) safety endpoints:

- Death
- Paralysis (excludes paraparesis)
- Myocardial Infarction
- Stroke (excludes TIA)
- Renal Failure (excludes renal insufficiency)
- Respiratory Failure (excludes COPD or pulmonary complications)
- Bowel Ischemia
- Lower Extremity Ischemia
- Procedural Blood Loss ( $\geq 1,000$  cc)

A MAE may or may not be considered related to the device. Mortality will be reported as “all cause” and “TAAA related.” All deaths occurring in the first 30 days post-index procedure are considered “TAAA related.”

The Clinical Events Committee (CEC) shall determine which adverse events in addition to those listed above in Section 8.11 are considered Major Adverse Events for evaluation of the primary (30 days) and secondary (1 year) safety endpoints.

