## 6.3 Treatment period (surgical procedure)

The following assessments and data collection will be performed at the time of the implant/surgical procedure:

- Investigational device accountability- documentation of product information (e.g., lot number, serial number)
- Exact measurements of position and configuration of custom made fenestrations
- Type of anesthesia
- Anticoagulation
- Description of delivery system access on both ipsilateral and contralateral sides (e.g. femoral cut down, percutaneous access, closure device)
- Volume of contrast used
- Total fluoroscopy time during procedure
- Estimated blood loss and replacement requirements
- Size of stents in visceral vessels
- Adjunctive procedures (e.g. stent placement)
- Investigator assessment of TAAA device performance as it relates to:
  - Access success/failure, delivery/deployment success, evidence of endoleak, device integrity issues
- Adverse events

The above events will be recorded on the **Procedure – System Evaluation CRF (either TEVAR alone or B TEVAR CRF)**

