### 9.1 Primary Endpoints

#### 9.1.1 Safety

The primary safety endpoint is the rate of major adverse events (MAE) at 30 days post branched TEVAR repair. The following specific events will be considered major adverse events: MAEs are defined as any one of the following events:

- Death
- Paralysis (excludes paraparesis)
- Myocardial Infarction
- Stroke (excludes TIA)
- Renal Failure (excludes renal insufficiency)
- Respiratory Failure (excludes COPD or pulmonary complications)
- Bowel Ischemia
- Lower Extremity Ischemia
- Procedural Blood Loss ( $\geq 1,000$  cc)

MAEs may or may not be considered related to the device. Mortality will be reported as “all cause” and “TAAA related.” All deaths occurring in the first 30 days post-index procedure are considered “TAAA related.”

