### 12.2 Clinical Events Committee

The Clinical Events Committee (CEC) will be used to review and adjudicate all device related adverse events and all serious adverse events regardless of the relatedness to the device. The

CEC shall also determine which adverse events (other than those listed in Section 9.1.1) are considered Major Adverse Events for evaluation of the primary and secondary safety endpoints. The committee shall consist of at least three (3) physicians representing multiple specialties familiar with thoraco-abdominal aortic aneurysm repair. The CEC will be comprised of Drs., [name], [name], [name] and [name]. [name] is a Professor of Surgery and Director of Surgical Critical Care at Harborview Medical Center. [name], is an Acting Instructor in the Department of Medicine and a member of the Medicine Consult Service at University of Washington Medical Center and the Seattle Cancer Care Alliance. [name] is a Clinical Professor with the Department of Pain and Anesthesia.. [name] PhD is an Associate Professor of Anesthesiology with expertise in the study of quality and safety. The CEC will provide their review to the DSM and will meet annually at a minimum.

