## **2.0 INTERIM ANALYSIS**

Interim analysis of the study is planned on an every six (6) month basis with the August Annual Progress Report serving as the starting point.

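### Sections 8.11 and 12.2 let the Clinical Events Committee add events to the primary 30-day MAE endpoint without criteria or a cut-off, so its composition can depend on the events observed

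*Protocol*

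**What the plan says.** The Protocol Summary makes the primary safety endpoint the proportion of subjects with an MAE within 30 days of B-TEVAR. Three sections then define an MAE.

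- **Section 9.1.1** uses closed wording, "MAEs are defined as any one of the following events", followed by nine events: death, paralysis, myocardial infarction, stroke, renal failure, respiratory failure, bowel ischemia, lower extremity ischemia, and procedural blood loss of at least 1,000 cc. It mentions no additions.
- **Section 8.11** gives the same nine, then states of the CEC that it "shall determine which adverse events in addition to those listed above in Section 8.11 are considered Major Adverse Events for evaluation of the primary" endpoint at 30 days, and likewise for the secondary endpoint at 1 year.
- **Section 12.2** restates the task by reference to the other list: "CEC shall also determine which adverse events (other than those listed in Section 9.1.1) are considered Major Adverse Events for evaluation". It too covers both the primary and the secondary endpoints.

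Section 12.2 also has the CEC "review and adjudicate all device related adverse events and all serious adverse events regardless of the relatedness to the device". Under Section 9.2.1 it meets annually to review all MAEs, and Section 12.2 makes annual meetings the minimum.

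**The concern.** A primary endpoint should be defined before its outcomes are known. Here the body that decides which further adverse events count is the body that reviews the accruing events. Nothing requires it to decide before it sees them.

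The clauses leave two further things open. They do not say what makes an event eligible for addition. They do not say whether an addition is an event type applied to every subject or a decision on a single case.

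Section 7.1 determines safety by the proportion of patients with MAEs, and Section 2.0 states the hypothesis that B-TEVAR carries fewer peri-operative complications than open repair. An MAE rate whose contents were partly settled during the study is hard to set against outside figures. Section 9.0 also calls for results by graft construct, and an event type added part-way or case by case could fall unevenly across the constructs.

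**Working it through.** The protocol states no expected MAE rate, performance goal, power or alpha for this endpoint, so there is no plan figure to reproduce. The check compares the text and then works out the size of one step.

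**1. The lists.** Sections 8.11 and 9.1.1 name the same nine events. The difference lies only in the power to add, which is present in 8.11 and 12.2 and absent from 9.1.1. Read together, the operative endpoint is nine events plus whatever the CEC adds.

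**2. Criteria and timing.** The other text on MAEs, the CEC and the safety monitor was searched: the Protocol Summary, Sections 8.9, 9.2.1 and 12.1, and Appendix IX. None of it gives a criterion for an addition, a date or data cut-off, or a reference to a committee charter.

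**3. Can additions depend on the data?** Three facts together allow it:
- the CEC sees all serious and all device-related events (12.2);
- it reviews all MAEs at least annually (9.2.1, 12.2);
- the study is non-randomized and single-institution (5.0), and Section 2.1.4 describes it as already using physician-modified grafts.

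**4. Size of a step.** Let *x* be the number of subjects with a listed event, *k* the number who count only through an addition, and *n* the number in the denominator.

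- Rate on the nine events: *x*/*n*. Rate with additions: (*x* + *k*)/*n*. Rise: *k*/*n*, which is never negative.
- *n* = 60 (Section 5.0): *k* = 1 gives 1/60 = 1.7 points; *k* = 3 gives 3/60 = 5.0 points; *k* = 6 gives 6/60 = 10.0 points.
- The 60 include patients planned for a two-stage repair (Protocol Summary), and Section 6.5 analyses those who never reach the second stage separately. The denominator can therefore fall below 60. Assumed values: *n* = 50 gives 1/50 = 2.0 points per subject; *n* = 40 gives 1/40 = 2.5 points.

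**5. Scale.** Suppose 12 of 60 subjects had a listed event (an assumption). The rate would be 20.0%, with an exact (Clopper-Pearson) 95% interval of 10.8% to 32.3%. Three added subjects would make it 15/60 = 25.0%, well inside that interval. The problem is one of definition more than precision.

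The value of *k* cannot be derived, because nothing in the protocol indicates what the CEC would add.

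**The case against.** The strongest case for leaving the text alone is that it is coherent. Section 12.2 cites 9.1.1 and the lists match, so 9.1.1 merely lacks a cross-reference. The power is conservative: the CEC may add events but is given no power to drop a listed one. Appendix IX says that the risks of the device are not currently known, which is a fair reason to let a committee recognise major events that nobody listed. The comparisons with outside series in Section 2.1 rest mainly on mortality and spinal cord injury. All-cause mortality, TAAA-related mortality and freedom from permanent spinal cord injury are separate endpoints in 9.2.1 that no addition can alter.

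All of this stands as a limit on the harm. It does not supply a criterion or a cut-off, and the protocol never says that the nine-event rate is the one to report as primary.

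A reader might also infer more than the text supports:

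- **A large shift.** One could picture paraparesis being added and apply the 20% and 31% temporary spinal cord injury rates from Section 2.1.4. But the list says "Paralysis (excludes paraparesis"), and a general power to add need not override an exclusion by name. Temporary injury is also not the same category as paraparesis, and the share of such injuries outside the listed event is not given.
- **Steering by interim results.** Appendix IX says "Interim analysis of the study is planned on an every six (6) month basis", but nothing says that the CEC receives those analyses. Section 12.2 describes the CEC passing its review to the safety monitor. The dependence on data rests on the CEC's own event review alone.
- **Loss of the nine-event rate.** Section 8.9 does not treat blood loss without transfusion as an adverse event, but Section 6.3 records blood loss at the procedure. How that item is captured is a separate question.

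**Conclusion.** The concern holds, with modest consequences. The protocol allows the composition of its primary safety endpoint to be settled after events have been reviewed, and 9.1.1 does not disclose this. It is not a flat contradiction between sections, because 12.2 shows that the additions are meant to sit on top of the 9.1.1 list. It is also more than detail that an analysis plan could supply, because the protocol itself makes the endpoint open-ended.

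The only supportable size is the step per subject: 1.7 points if all 60 are in the denominator, and more if fewer receive B-TEVAR. No inflated error rate or reversed conclusion can be claimed, since no test or performance goal is stated and additions can only raise the rate. What suffers is pre-specification and the interpretability of the 30-day MAE rate. A CEC charter may hold criteria, but the protocol refers to none. The point should be fixed, and it is not critical in a feasibility study.

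**What to change.** Put one identical statement in Sections 8.11, 9.1.1 and 12.2, replacing the sentences in 8.11 and 12.2 that let the CEC add events. Suggested wording: *The primary and secondary MAE endpoints comprise only the nine events listed in Section 9.1.1. The CEC adjudicates whether a reported event is one of these nine. Any other event that the CEC judges to be major is reported in a separate supplementary table, defined by event type and applied to all subjects.*

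The committee can still recognise unforeseen major events, and reporting of serious adverse events, unanticipated device effects and deaths (Sections 8.10, 8.12 and 8.15) is untouched.

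The cost is two amended sentences, one short addition and matching instructions to the CEC. There are two downsides. A newly recognised major event type would appear beside the primary endpoint and not inside it. As a change to the investigational plan, the amendment also needs prior IRB and FDA approval under Section 11.8.
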